- b. Justification and safety information if FDA approved drugs will be administered for non-FDA approved indications or if doses or routes of administration or participant populations are changed.

N/A

- c. Justification and safety information if non-FDA approved drugs without an IND will be administered.

N/A

8. Study Statistics

Outcome Measures: We will collect a variety of outcome measures to enable a full characterization of decision-making factors at baseline, and the impact of this intervention on smoking status, postsurgical outcomes, opioid analgesia utilization, and cost.

- a. Primary outcome variable.

Smoking Outcomes: Our primary outcome variable will be smoking status. Smoking abstinence will be defined as a negative biochemical sample + self-report of no smoking for the past 7 days, mean % negative samples, and mean continuous negative samples. Smoking will be evaluated within each pre and post-surgical phase, and collapsed over the 11-week targeted cessation period (following the TQD during week 2). Point prevalence smoking abstinence at the follow-up will be defined as a negative cotinine sample + self-report of no smoking for the past 7-days.

b. Secondary outcome variables.

Secondary smoking outcomes will include ratings of nicotine withdrawal and craving, using standardized measures, and frequency of adverse events judged to be related to varenicline or smoking cessation.

Surgical Recovery Outcomes: A variety of postsurgical outcomes will be evaluated. These will include length of hospital stay, overall quantity and frequency of opioid analgesic use, pain ratings of during the recovery period, types and frequency of post-operative complications, frequency of admission into the intensive care unit, and 30-day hospital readmission rates.

c. Statistical plan including sample size justification and interim data analysis.

Since this is an open-label study design, results will be analyzed in a mostly descriptive method.

Smoking Outcomes: Smoking outcomes will be evaluated as a function of time over the 11-week intervention. Smoking cessation rates will also be compared from the pre to post-intervention phases.

Surgical Recovery Outcomes: Surgical outcomes will be evaluated as a function of percent biochemically-confirmed smoking abstinence, to assess whether the duration and/or magnitude of smoking abstinence is statistically associated with 30-day readmission rates, opioid analgesic use, and other surgical outcomes.

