Study-related Measures: We will generate summary scores for each of the study measures and evaluate whether baseline values were positively associated with smoking outcome, and whether there were any changes in measures over time as a function of smoking status. These data will be used to help identify which measures may be most sensitive to change over time for a full-scale trial.

Sample Size Considerations: Our proposed sample of 20 completers is consistent with other open label studies of this kind. Additionally, our pilot data on bariatric patients from FY 2014 included only 23 smokers and still provided enough power to show a signal regarding the effects of smoking status on duration of hospital stay, total costs, and 30-day hospital readmissions. As such, we believe 20 completers will be a large enough sample to demonstrate an effect of the intensive intervention on promoting smoking cessation and minimizing post-surgical complications, and will also be a feasible sample size to recruit within the 2-year study period.

d. Early stopping rules.

This study will be stopped if we have evidence that enrolling participants into the study puts them at undue risk of experiencing complications during their surgery. We do not anticipate this happening, however since this is the first study of its kind in this population, we will monitor the data closely to verify safety of the participants.

9. Risks

a. Medical risks, listing all procedures, their major and minor risks and expected frequency.

Varenicline Administration:

Side-effect risks associated with varenicline administration (21): Allergic reactions to varenicline can be life-threatening and are generally characterized by a swelling of the face, mouth, and throat that can cause trouble breathing. *GI*: Nausea is the most frequent side-effect of varenicline and is present in approximately 30% of participants taking varenicline (versus 10% of participants taking placebo). The nausea associated with varenicline is generally transient, dose-dependent, of moderate intensity, and leads to dose discontinuation in only 3% (0.6% - 9%) of people who begin taking varenicline. Constipation, flatulence, and vomiting are more rare but possible side-effects. *Sleep complaints*: Insomnia (12% in

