Hospitalization for Non-study Related Injury or Illness: It is likely and expected in this study that some participants will be rehospitalized while still enrolled in the study. We anticipate these hospitalizations will be related to their surgery and will be generally unlikely they will be related to study participation. Nevertheless, in the event of a confirmed hospitalization, study and medical staff will evaluate the event and determine whether it meets criteria for immediate reporting. Events that meet these criteria will be promptly reported to the IRB and NIH in accordance with reporting guidelines of severe adverse events (SAE). The medical monitor of the study will determine whether it is safe for the participant to remain on the study medication or resume its use based upon the specific adverse event.

Pregnancy: There is risk that female participants may become pregnant while enrolled in the study and taking varenicline. Varenicline has been assigned to pregnancy category C drug, indicating there are no adequate and well-controlled studies in humans to assess the safety of varenicline in pregnant women, and therefore is contraindicated for women who are pregnant or breastfeeding. Female participants who plan to become pregnant or who refuse to use adequate methods of birth control during the study will be excluded. Female participants will be tested for pregnancy monthly and if found to be pregnant will be discontinued from the study and varenicline will be stopped immediately.

Questionnaires and Decision-Making Tasks: Minimal risks associated with completing the questionnaires and decision-making tasks are subject fatigue and the possibility of minor psychological distress associated with answering sensitive questions regarding psychological functioning. Participants will be informed that they may choose not to answer any questionnaires that cause discomfort.

Violation of Confidentiality: The risk of violation of confidentiality exists because human subjects are giving personal information.

b. Steps taken to minimize the risks.

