Protection Against the Emergence of Neuropsychiatric Symptoms: The most worrisome potential side-effects of varenicline is the occurrence of rare neuropsychiatric symptoms (suicidal thoughts). Monitoring for such potential side effects will take place via multiple mechanisms. First, participants will be screened with specific questionnaires to history of suicidal thoughts and/or behaviors. Participants with severe prior or current psychiatric symptoms such as psychosis, suicidal behaviors, will be excluded from the study. Second, eligible participants will be informed of the risks for neuropsychiatric side effects and will be instructed to inform a study staff member immediately following any observed change in mood or worrisome thoughts, and will be assessed as clinically indicated. Third, trained staff members will meet with participants on a weekly basis to assess for adverse events using open-ended questions, as well as any emergency room visits and/or hospitalizations that may have occurred. Medical staff will be consulted if the participant endorses any behaviors or thought patterns that signify threats to patient safety or the safety of others, or any adverse event requiring medical attention including vital signs that are out of the norm. Adverse events will be reported to the IRB and the funding agency in accordance with reporting guidelines, and will be recorded as secondary outcome measures. Participants will complete a weekly assessment and the BDI at each study visit. Any endorsement of suicidal thoughts (at any level) on the BDI will prompt administration of the more comprehensive C-SSRS measure to fully characterize suicidal ideation. Any changes in weekly updates, regarding agitation, sadness, or hostility will also prompt assessment by a trained and qualified study investigator. A psychiatrist is always available to assist study staff in the evaluation and management of individual cases. In addition, the Emergency Department and Community Psychiatry department are located on the same campus as the BPRU smoking cessation clinic and are available to provide additional care to participants as needed. Following endorsement of any past 30 day suicidal ideations and/or behaviors, or if determined otherwise necessary by a trained member of the study staff, the individual will be escorted by a staff member to the Emergency Room (located across the street from the BPRU) for further evaluation and/or treatment. Participants will be reminded that they can stop

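### Sections 8.b and 9.b disagree on whether the adverse-event outcome is limited to related events, and the one stated stopping criterion in 8.d does not match the plan's own outcomes and risks

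*Combined protocol and SAP*

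**What the plan says.** **Adverse-event outcome.** Section 8.b (Secondary outcome variables) lists, among the secondary smoking outcomes, the "frequency of adverse events judged to be related to varenicline or smoking cessation". Section 9.b (Protection Against the Emergence of Neuropsychiatric Symptoms) words it differently: "Adverse events will be reported to the IRB and the funding agency in accordance with reporting guidelines, and will be recorded as secondary outcome measures". The second statement has no relatedness condition.

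**Surgical outcomes.** Section 8.b also lists "types and frequency of post-operative complications, frequency of admission into the intensive care unit, and 30-day hospital readmission rates", again without a relatedness condition. Section 8.c analyses the surgical outcomes as a function of percent confirmed abstinence.

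**Expectation about cause.** On hospitalizations during the study, section 9.a states "We anticipate these hospitalizations will be related to their surgery" and regards a link to study participation as generally unlikely. Section 5.c confirms that there is no comparison condition.

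**Study-level stopping.** Section 8.d gives one criterion: the study stops if there is evidence that enrolling participants "puts them at undue risk of experiencing complications during their surgery". It adds "we will monitor the data closely to verify safety of the participants", without tying that monitoring to a stopping decision. It gives no threshold, review time or deciding body.

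**The concern.** The two descriptions of the adverse-event outcome can produce different safety tables from the same data. Under 8.b someone must first decide whether each event was caused by varenicline or by quitting. That person knows every participant is on the drug and has no control rate to compare with. For hospitalizations, the protocol has also recorded in advance which cause it expects.

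The judgement is hardest after surgery. Nausea, vomiting, constipation and insomnia are listed varenicline effects in section 9.a, and they could plausibly also follow an operation or opioid use. The study is meant to support a larger randomised trial (section 2), which will need a safety count that can be interpreted without knowing how each attribution was made.

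The stopping criterion raises a separate question of scope. Read literally, it looks only at the operation itself. The harms that the protocol describes at most length, and the surgical outcomes that it plans to measure, mostly arise before or after it.

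**Working it through.** The plan states no figure on this point that could be reproduced, so the check is mainly a comparison of text.

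**1. Which events enter the adverse-event count?**

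| Event | Under 8.b | Under 9.b |
|---|---|---|
| Judged related to varenicline or cessation | counted | counted |
| Judged unrelated, including a neuropsychiatric event | not counted | counted |
| Post-operative complication, ICU admission, 30-day readmission | separate outcome, unfiltered | separate outcome, and also an adverse event if recorded as one |

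The conflict is confined to the second row. The third row shows that surgical events stay in the results either way, although 8.c relates them to abstinence and does not plan them as a safety summary.

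**2. What does one exclusion do?** Assume a denominator of the 20 completers in section 8.c.
- One participant is 1/20 = 5 percentage points of incidence.
- With 0 of 20 affected, the exact one-sided 95% upper bound solves (1 − p)^20 = 0.05, so p = 1 − 0.05^(1/20) = 13.9%.
- With 1 of 20 affected, it solves (1 − p)^20 + 20p(1 − p)^19 = 0.05, so p = 21.6%.

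Moving one participant across the relatedness line therefore changes the rate that the study can exclude from 21.6% to 13.9%. The documents give no basis for saying how often this would happen.

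**3. Will attribution questions arise?** As context, take the 30-day readmission rates in Table 1 (section 4) and assume that they carry over from bariatric patients to this sample.
- At the smokers' 17%: 20 × 0.17 = 3.4 expected; P(at least one) = 1 − 0.83^20 = 97.6%.
- At the nonsmokers' 4%: 20 × 0.04 = 0.8 expected; P(at least one) = 1 − 0.96^20 = 55.8%.

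Hospitalizations needing a causal judgement are thus likely. For neuropsychiatric events the documents say only that they should be rare. At assumed rates of 0.5% to 5%, P(at least one in 20) runs from 1 − 0.995^20 = 9.5% to 1 − 0.95^20 = 64.2%.

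**4. What does the stopping criterion cover?**

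| Named in the plan | Where | Stated study-level trigger in 8.d? |
|---|---|---|
| Complications during surgery | 8.d | yes |
| Post-operative complications, ICU admission, readmission | 8.b | no, read literally |
| Neuropsychiatric symptoms, ranked the most worrying potential side effect | 9.b | no |
| Cardiovascular events, with conflicting evidence cited | 9.a | not outside the operation |
| Allergic reactions, described as potentially life-threatening | 9.a | not outside the operation |

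The outcomes named in 8.b include no event specific to the operation itself. The other stopping provisions act on individuals: withdrawal for psychiatric symptoms (5.f), the medical monitor's decision on a participant's medication after hospitalization (9.a), and further suicidality assessment with emergency referral (9.b).

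**The case against.** Several points on the other side stand.

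- A reader might infer that post-operative harms vanish from the results. They do not: 8.b lists complications, ICU admission and readmission without a filter.
- A reader might infer that mood and side-effect information is lost with the filter. Section 5.a collects the BDI at every visit, the C-SSRS throughout and a weekly side-effect measure, none of which needs an attribution. Section 8.c plans summary scores and change over time for the study measures.
- A reader might infer that neuropsychiatric or post-operative events can never stop the study. The text does not say so. Section 8.d does not call its criterion exclusive and promises close monitoring. Sections 9.a to 9.c send serious events and unanticipated problems to the IRB and, for serious events, to NIH. The phrase about surgery may also be loose wording for the perioperative period.
- It is tempting to treat all post-surgical drug exposure as uninformative, or to let every case of nausea swing on attribution. Neither is supported. Section 9.a expects staff to evaluate each confirmed hospitalization, and its stated expectation concerns hospitalizations only. Section 9.a also calls nausea generally transient, and dosing starts about 4 to 6 weeks before surgery, so nausea that begins then cannot be blamed on the operation.
- This is a small, mostly descriptive pilot, and a formal safety analysis would be out of proportion.

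These points limit the concern but do not remove it. The 8.b and 9.b wordings still differ, and the scales complement an adverse-event table without replacing it. Reading the stopping criterion as perioperative would still leave neuropsychiatric events before that period unnamed.

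**Conclusion.** Two textual defects hold.

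First, 8.b and 9.b conflict on the adverse-event outcome. If 8.b governs, the reported frequency depends on an unblinded judgement that cannot be checked against a comparison rate, and events judged unrelated can be left out of the count. The size per participant is 5 percentage points, assuming 20 in the denominator. The total effect and its direction cannot be estimated from the documents. The stated expectation about hospitalizations gives a reason for care, but it is not proof of bias.

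Second, the single study-level criterion stated in 8.d does not match the post-operative outcomes in 8.b or the neuropsychiatric, cardiovascular and allergic risks in section 9. The supported conclusion is that these are not stated triggers. It does not follow that the study could not be stopped for them.

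The readmission and rare-event probabilities in the working are context only and rest on the rates assumed there.

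**What to change.** In 8.b, define the adverse-event outcome as all adverse events, reported separately for the pre-surgical and post-surgical phases, with relatedness shown as an added column and not used as a filter. This agrees with 9.b. Adverse events are already to be collected at the study visits, so no new data are needed. The cost is a wording change, one more table split and a higher reported count, because events attributed to surgery will appear in it.

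Separately, the sponsor should reconcile 8.d with 8.b and section 9, so that the stopping section, the outcomes and the named risks describe the same scope. What that scope should be, and any threshold, are for the sponsor to decide; no particular stopping rule is proposed here.

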- Questionnaire of Smoking Urges-Brief (QSU-B; Cox et al., 2001): 10-item self-report measure with good reliability and validity for detecting cigarettes craving.
- Medication Adherence Questionnaire (MAQ; Morisky et al., 1986): 4-item self-report measure used to identify potential problems with adherence to a medication regimen including quit smoking aid pharmacotherapies (Toll et al., 2007). Will be given monthly to monitor self-reported compliance with study medication.
- Beck Depression Inventory (BDI, Beck et al., 1961): 21-item self-report measure that evaluates symptoms of depression and suicidal thoughts. Scores are aggregated and categorized as minimal (0-13), mild (14- 19), moderate (20-28) or severe (29-63) depression. Participants who score >20, indicating moderate to severe depression, or who endorse >0 on the suicidal thoughts question (item 9) during screening will be excluded and referred to a clinician for further evaluation and referral if indicated. The BDI will be administered at every study visit to assess ongoing changes to mood.
- Columbia Suicide Severity Rating Scale (C-SSRS; Posner et al., 2003): The C-SSRS is a widely used suicide rating scale that is frequently used in clinical trials that administer varenicline. The C-SSRS will be used at baseline to assess lifetime history of suicidal events, and throughout the study.
- Weekly Update: We will administer a measure designed to assess changes in potential varenicline-mediated side effects over time at every weekly visit. This measure was designed in the context of large-scale trial to assess varenicline for alcohol treatment and was used successfully in a recently completed study to assess varenicline for smoking cessation (NA_00074143).
- Adverse Events Questionnaire: Locally developed measure to query potential side effects and concomitant medications. Specific questions address concerns with new onset of irritable and potentially violent behaviors.

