Following the surgery, patients will resume weekly study visits approximately two weeks post-surgery in order to continue with the post-surgical varenicline administrations and to assess post-surgical recovery and smoking cessation outcomes. We will attempt to coordinate with the surgery team to schedule patients' first post-surgical study visit on the same day as their two-week post-surgical follow-up visit with their surgeon

in order to maximize convenience for patients, and participants will be given a 2-week supply of varenicline at the study visit immediately prior to their scheduled surgery so that they can continue taking the full dose while recovering from surgery. Patients will return weekly for a total of six post-surgical study visits. Additional follow-up may occur for six months post-intervention. More details about timing of each of the intervention components are listed below:

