2. Varenicline: Varenicline will be administered as clinically indicated and will begin approximately 4-6 weeks prior to surgery. All participants will receive a 1-week dose induction period (0.5mg QD Days 1-3, 0.5mg BID Days 4-7) before transitioning to a full maintenance dose (1mg BID). The target-quit date (TQD) will be on Day 8 (week 2) and will coincide with the 1st day of the maintenance dose, consistent with recommended guidelines. Participants will receive a 1-week supply of varenicline (with 3 days of extra doses in the event of an unpredicted event) in blister packs at each study visit. This will enable us to better track medication adherence and adverse events, and will help encourage participants to attend weekly visits. There is nothing experimental about the use of varenicline in this study. Participants will receive a 2-week supply of varenicline (with 3 days of extra doses) at the visit immediately prior to the participants’ scheduled surgery in order to allow participants to continue taking the full maintenance of varenicline uninterrupted, while also allowing for ample healing time before returning for the first study visit post-surgery.

3. Incentives: Incentive payments will begin on the TQD (week 2) and will be in place for 5 weeks or until surgery (whichever is sooner). Participants will receive monetary based incentives for biochemical evidence of smoking abstinence. Abstinence will be determined via breath carbon monoxide (CO) ratings during Week 2, and via urinary cotinine for the duration of the study. The transition from CO to cotinine is a common procedure that provides a method for awarding incentives to participants who have recently begun abstaining from smoking but will still test positive for cotinine (because of the long elimination half-life of cotinine). Cotinine-based testing will be used as the definition of abstinence during weeks 3-12. CO will be tested using mobile meters and abstinence will be

Table 2. Incentive and Compensation Structure

Study Week	Study Visit	Incentives	Visit Payments
Screening			\$30
1	-6		\$20
2	-5	\$20	\$20
3	-4	\$40	\$20
4	-3	\$60	\$20
5	-2	\$80	\$20
6	-1	\$100	\$20
7	1		\$50
8	2		\$60
9	3		\$70
10	4		\$80
11	5		\$90
12	6		\$100
Follow-up			\$50
Total:		\$300	\$650

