Study Visits: Participants will attend an initial in-person screening visit, described above, and will return to the clinic on approximately a weekly basis during study weeks 1-12 to receive the intensive pre- post-surgical smoking cessation intervention. Visits during the surgical week will occur prior to the surgery to allow for postsurgical recovery time and we will provide 2 weeks of medication at that visit to allow participants to continue using the medication during their recovery period and provide general flexibility to participants who are unable to complete a visit during their first postsurgical week. Each visit will include collection of a urine sample (that will be tested for urinary cotinine and illicit drug use), a breath CO sample, and self-report questionnaires. None of the data collected during study visits will be shared with the patients' surgical team. Participants will be contacted via phone approximately 3 weeks after study

completion and asked whether they are still abstaining from smoking. Those who endorse continued abstinence will be asked to complete a follow-up visit, during which they will provide a urine sample that will be tested for evidence of cotinine. Participants may be contacted over an additional six month period for follow-up questions pertaining to treatment outcome. Participants will be compensated for attending study visits and completing brief questionnaires and tasks; session payment values will escalate after surgery to encourage continued retention (a standard practice in our treatment protocols) and the total possible study visit compensation will be \$650.

- c. Blinding, including justification for blinding or not blinding the trial, if applicable.

Given that this is an open-label pilot study, all participants will receive the same intensive pre to post-surgical smoking cessation intervention in order to collect the data necessary to illustrate the feasibility of incorporating such an intensive intervention into the hospital setting. This pilot data will be used to support the need for future funding to complete larger randomized controlled trials, and/or multi-site trials. Given that no comparison condition is being included in the current pilot study, the issue of blinding is not applicable at this time.

- d. Justification of why participants will not receive routine care or will have current therapy stopped.

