varenicline versus 10% in placebo group), and vivid or abnormal dreams. *Neurologic*: headache. *Cardiovascular*: A meta-analytic review concluded that varenicline increased the risk of cardiovascular events compared to placebo (22), however a clinical trial demonstrated that varenicline was safe for use in patients with stable cardiovascular disease (23) and an updated meta-analysis concluded that varenicline did not increase the risk of cardiovascular adverse events (24).

Psychiatric risks associated with varenicline: Cigarette smoking itself has been associated with suicidality, and there have been concerns raised regarding whether smoking cessation aids (including varenicline) increase the risk of depression and suicidal ideation and/or behavior (25). A series of case studies also reported a trend towards impulsive and unpredictable aggressive behavior among patients receiving varenicline for smoking cessation (26). These concerns prompted several meta-analytic reviews of psychiatric events following varenicline administration; all three meta-analyses concluded there was no increased risk of psychiatric events following varenicline administration for smoking cessation (26-29). A further, prospective study also reported no emergence of aggressive events among people receiving varenicline for smoking cessation (30). Therefore, though the incidence of neuropsychiatric symptoms among patients taking varenicline are of serious concern, they are expected to be rare.

Potential Drug-Drug Interactions: There is a general risk that varenicline might have an adverse reaction with another medication. The only known interactions for varenicline is bupropion (Wellbutrin, Zyban), and we will exclude all participants taking bupropion (which is another potential smoking cessation medication) from this study.

Smoking: It is possible that participants may not respond to the intervention and may continue to smoke cigarettes. Smoking incurs health risks in general and increases the risk of poor recovery, specific surgery-related side effects post-surgery, and decreased sensitivity/response to narcotic pain medications.

Discomfort from Pain Testing: Participants will likely find the pain testing procedures uncomfortable for a brief period of time. This effect is expected to be transient and to produce only mild levels of discomfort.

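### Weekly staff adverse-event checks are promised without a surgical exception, but the text on visit timing allows about 14 days on full-dose varenicline with no scheduled contact, and the documents disagree on when visit 1 occurs

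*Combined protocol and SAP*

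**What the plan says.** **The promise.** Section 9.b (Protection Against the Emergence of Neuropsychiatric Symptoms) calls rare neuropsychiatric symptoms, meaning suicidal thoughts, the most worrisome potential side effect of varenicline. Its third listed mechanism is that "trained staff members will meet with participants on a weekly basis to assess for adverse events using open-ended questions". The same paragraph ties the BDI to each study visit and uses any endorsement of suicidal thoughts on it to trigger the C-SSRS. Section 5.a (Screening and Study-related Measures) says of the Weekly Update: "We will administer a measure designed to assess changes in potential varenicline-mediated side effects over time at every weekly visit".

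**The restart after surgery.** Section 5.a (Intensive Smoking Cessation Intervention) says "patients will resume weekly study visits approximately two weeks post-surgery", and staff will try to place the first of these visits on the day of the surgeon's two-week follow-up. Section 5.a (Varenicline) provides a 2-week supply plus 3 days of extra doses at the last visit before surgery, to let participants "to continue taking the full maintenance of varenicline uninterrupted, while also allowing for ample healing time".

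**Text pointing to an earlier visit.** "Table 2. Incentive and Compensation Structure", repeated in Section 11, puts visit -1 in study week 6 and visit 1 in week 7. Section 5.b says participants "will return to the clinic on approximately a weekly basis during study weeks 1-12". It places the surgical-week visit before the operation and explains the 2-week supply partly as a way to "provide general flexibility to participants who are unable to complete a visit during their first postsurgical week".

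**The concern.** The weekly meeting is the only one of the three listed mechanisms in which staff actively look for symptoms throughout treatment. The first is screening at entry, and the second is an instruction to participants to report changes themselves. If visits restart two weeks after surgery, the meeting lapses while dosing continues at 1 mg BID. The BDI, its link to the C-SSRS and the Weekly Update lapse with it, because all of them are tied to visits. The only scheduled telephone contact in the protocol comes about three weeks after study completion (Section 5.b).

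At stake is how soon a change in mood or suicidal thinking would be found in someone recovering from surgery, possibly at home. Section 8.d says the data will be watched closely because this is the first study of its kind in this population, which makes a lapse right after surgery hard to justify. Staff also cannot tell from the documents whether a visit in the first postsurgical week is expected or optional.

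**Working it through.** **Inputs**

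- Promised interval between staff checks: 7 days (Section 9.b).
- Drug course: 12 weeks (Section 7.a), so 12 × 7 = 84 days.
- Visit 1: about 14 days after surgery (Section 5.a text), or study week 7 (Table 2).
- Days from visit -1 to surgery: not stated; call this *k*. Section 5.b says only that the surgical-week visit comes before the operation.

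**Table 2.** Visit -1 is in week 6 and visit 1 in week 7, so the interval is 7 days and 7/7 − 1 = 0 checks are missed.

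**Section 5.a text.** The interval is *k* + 14 days, the excess over the promise is *k* + 14 − 7, and the checks missed are (*k* + 14)/7 − 1.

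| *k* (assumed) | Interval | Excess | Excess / 84 | Checks missed |
|---|---|---|---|---|
| 0 | 14 days | 7 days | 8.3% | 1.0 |
| 3 | 17 days | 10 days | 11.9% | 1.4 |
| 6 | 20 days | 13 days | 15.5% | 1.9 |

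The row *k* = 0 needs the fewest assumptions and is the figure used here. The other rows show the direction if the last visit comes earlier.

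**Do the two schedules match on the calendar?** Take weekly visits from day 1. All days are nominal, because the plan calls its timings approximate.

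- Six presurgical visits fall on days 1, 8, 15, 22, 29 and 36. Table 2 then puts visit 1 on day 43 (week 7) and visit 6 on day 43 + 35 = 78 (week 12). The two-week restart with *k* = 0 puts visit 1 on day 36 + 14 = 50 (week 8) and visit 6 on day 50 + 35 = 85 (week 13).
- With five presurgical visits, visit -1 is day 29. The two-week restart gives visit 1 on day 29 + 14 = 43 (week 7) and visit 6 on day 78 (week 12), which agrees with Table 2's postsurgical weeks.

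The overrun into week 13 therefore needs six full presurgical visits, and it amounts to one nominal day (85 against 84). The 14-day interval between checks is present in both cases.

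**The case against.** The strongest reply is that Section 9.b is a general paragraph on risk, while Sections 5.a and 5.b openly describe a pause around surgery, give healing and convenience as reasons, and call visits approximately weekly. The specific text then qualifies the general, and only a cross-reference is missing. In addition, Section 5.b can be read as making a first-week visit the norm and the longer supply an allowance for those who cannot attend. On that reading the schedule keeps the promise.

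Part of this stands. A definite lapse for every participant is not established, because it depends on which schedule is followed. But a pause that doubles the interval and is linked to a two-week appointment is more than looseness in the word approximately. If the earlier visit is intended, the Section 5.a text needs correcting. If the pause is intended, the safeguard has an exception that Section 9.b does not disclose.

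Other protections also remain:

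- participants are told to report mood changes at once, and a psychiatrist is available (Section 9.b);
- endorsement of suicidal thoughts or behavior in the past 30 days leads to emergency evaluation (Section 9.b), a window that would cover even a 20-day interval once the participant is seen;
- confirmed hospitalizations are reviewed (Section 9.a), and there are record access and a medical card (Section 9.b);
- the Daily Diary records negative mood and stress (Section 5.a), though no review between visits is described.

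These reduce the risk. They rely mostly on the participant or the hospital acting first, or they take effect only at the next visit, so they do not replace a scheduled staff check.

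**Conclusion.** The point holds as an unresolved conflict over visit 1, together with a lapse in a stated safeguard whenever the two-week restart is followed. In that case the interval is about 14 days against 7: an excess of about 7 days, 8.3% of the course, and at least one check missed. This assumes the last visit is on the day of surgery; an earlier last visit lengthens it. Under Table 2 nothing is missed.

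The consequence is limited to possible late detection of a rare event. Section 9.a says that "though the incidence of neuropsychiatric symptoms among patients taking varenicline are of serious concern, they are expected to be rare", and participants will have had roughly 4 to 6 weeks of dosing with weekly visits before surgery.

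A reader might infer four stronger things that the documents do not support:

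- **That a sixth of treatment goes unmonitored.** 14/84 = 16.7% counts the whole interval, although perfect weekly visits also leave 7 days between checks.
- **That two checks are lost over 20 days.** This rests on assuming a last visit 6 days before surgery. The 14 + 3 = 17 days of drug supplied at that visit suggests an interval nearer two weeks was planned.
- **That the schedule overruns the 12 weeks.** This depends on six full presurgical visits and is one nominal day.
- **That adverse events, a secondary outcome in Section 8.b, will be undercounted.** No undercount is shown: the staff interview also asks about emergency visits and hospitalizations that may have occurred.

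This is a worthwhile low-cost safety improvement. It does not affect the planned, mostly descriptive, analysis.

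**What to change.** Keep the healing pause, and make these changes:

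1. State once when visit 1 occurs relative to surgery, and bring Section 5.a, Section 5.b and Table 2 (with its copy in Section 11) into line.
2. In any perioperative week without a visit, have existing staff make one brief telephone or inpatient check. It should use the open-ended adverse-event questions and the BDI suicidality item, with the C-SSRS if that item is endorsed.
3. Write down the response to a positive answer given remotely: the on-call psychiatrist, or emergency or community referral along the lines of Section 9.b. The present response, a staff escort to the nearby emergency room, does not work by telephone.
4. Have the adverse-event questions at visit 1 cover all time since the last visit.

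The cost is about one call per participant, 20 × 1 = 20 short calls for 20 completers, and somewhat more if the last visit falls well before surgery. Add a short remote-response procedure and a few lines of protocol text. Section 5.b already uses telephone contact for follow-up, so the method is not new to the study.
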